This study will be a large, multi-center, randomized prospective trial for TAP block, evaluating postoperative pain, PONV, hospital stay and other surgical outcomes.

Study Population and Design

The study design will be a multi-center, double-blinded, prospective, randomized controlled trial comparing Marcaine (bupivacaine) with normal saline in a transversus abdominis plain block in adult patients who have undergone elective laparoscopic colorectal surgery.

The purpose of this study will be to prove the effectiveness of local anesthetic given via a TAP block in improving postoperative pain, postoperative opioid use, PONV and surgical outcomes such as hospital length of stay in laparoscopic colorectal surgery when compared to controls.

The study will randomize adult patients with benign and malignant conditions of the colon and rectum that require elective laparoscopic right, total, and left colectomy into two groups. Subjects meeting the inclusion criteria will be informed about the trial, and requested to participate after the informed consent process.

Recruitment

The patients will be recruited from the Departments of Colorectal Surgery of University Hospitals of Cleveland OH as well as approximately 3 to 6 other institutions across the United States. The patient population in this study will be candidates of either sex, over 18 who have benign or malignant colonic or rectal disease in which resection is required via a laparoscopic approach. The patients will be asked to participate in the study after evaluation by either the PI or the co-investigators and candidacy for either procedure has been established. The investigator will discuss the study with the patient and the study coordinator will participate in patient recruitment. Patients will be recruited until at least 75 participants are enrolled from all institutions, with up to 75 patients enrolled from UHCMC if other institutions do not participate.

Inclusion criteria:

1. Subjects who have benign or malignant colonic or rectal disease that are being scheduled for laparoscopic colorectal resection.
2. Subjects who are 18 years of age and older
3. Subjects of either sex
4. Subjects who are willing and able to adhere to protocol requirements, agree to participate in the study program and provide written and informed consent.

Exclusion criteria:

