Subject charts and clinical records will be requested and reviewed so that protocol adherence and source documentation can be verified. Information collected from the medical file will be entered into a study spreadsheet to collect data on each subject. The data collection spreadsheet will be kept password protected on Shared Drive in the Department of Surgery in which the principal investigator and the study coordinator have access. Initials will only be used along with surgery date. A separate spreadsheet will be kept of the subject's date of surgery and patient number will be kept on the study coordinator's hard drive in which only she has the password. All data collection forms will be kept under lock and key in the Department of Surgery. Only members of the research team will have access to the documents. The information will only be disclosed with the subject's permission or as required by law. Upon publication, no subjects will be identified and all information will be reported conclusively. There is a possibility that the University Hospitals of Cleveland Institutional Review Board, Food and Drug Administration and possibly foreign regulatory agencies may review the study records.

Data analysis/statistics

Routine statistical analyses will be utilized for parametric and non-parametric datasets, as appropriate. Demographic data will be analyzed using students t-test or Fishers exact test as appropriate. Repeated measurements (pain, nausea scores) will be analyzed by repeated measures ANOVA or ANOVA on ranks. Further paired comparisons at each time interval will be analyzed using the t-test or Mann-Whitney U-test as appropriate. Categorical data will be analyzed using χ^2 analysis or Fishers exact test where applicable. Normally distributed data will be presented as means \pm SD of the mean, non-normally distributed data will be presented as medians \pm quartiles and categorical data will be presented as raw data and frequencies. A P value of > 0.05 will be considered statistically significant.

References

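### The only significance rule in the plan is reversed: it counts P values above 0.05 as significant

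*Combined protocol and SAP*

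**What the plan says.** The last sentence of the Data analysis/statistics section reads: "A P value of > 0.05 will be considered statistically significant". It is not limited to any endpoint or test, so it governs everything named before it in that section: the t-test, Mann-Whitney U-test, repeated measures ANOVA, ANOVA on ranks, chi-square and Fisher's exact test. For example, the follow-up comparisons of pain and nausea scores are specified as "Further paired comparisons at each time interval will be analyzed using the t-test or Mann-Whitney U-test as appropriate", and their results would be judged by this rule.

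The aim, under Study Population and Design, is one of superiority over saline: "The purpose of this study will be to prove the effectiveness of local anesthetic given via a TAP block in improving postoperative pain". The same sentence extends the aim to opioid use, postoperative nausea and vomiting (PONV) and surgical outcomes such as length of stay.

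The document gives no other alpha, no confidence level, no statement of sidedness and no power calculation.

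**The concern.** A P value measures how surprising the data would be if the treatment made no difference, so small values count against the null hypothesis. The rule as written labels as significant the results that are compatible with no difference, and withholds the label from those that contradict it. A reversed inequality in background text would be harmless. Here it sits in the one sentence that says how the trial will separate an effect from chance.

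The intended rule also cannot be recovered from elsewhere in the document. A sample size calculation would normally restate the alpha and the sidedness, but there is none. Every inferential statement on pain, opioid use, PONV and length of stay therefore depends on a criterion that has to be set aside before it can be used.

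**Working it through.** **Inputs from the document**
- Rule: significant if P > 0.05 (Data analysis/statistics).
- Hypothesis: superiority of bupivacaine over saline (Study Population and Design). No equivalence or non-inferiority margin is given.
- Sample size: "Patients will be recruited until at least 75 participants are enrolled from all institutions" (Recruitment).
- Two groups, with no allocation ratio stated (Study Population and Design).

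**Assumptions, because the document is silent**
- Two-sided tests.
- Equal allocation, so 37 and 38 patients.
- A continuous outcome compared by t-test, with standardised differences *d* from 0.3 to 1.0.

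The plan has no power figure to reproduce, so the check is of the error rates that the rule implies.

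**Step 1: no true effect.** For a continuous outcome the P value is uniform on 0 to 1 under the null. Hence Pr(P > 0.05) = 1 − 0.05 = 0.95. The type I error per test is 95% under the rule as written and 5% under the conventional one. A simulation of 40,000 t-tests with 37 against 38 patients gave 95.2% and 4.8%.

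**Step 2: a true effect.** The t statistic has 37 + 38 − 2 = 73 degrees of freedom, with a two-sided 5% critical value of 1.993. Its noncentrality is *d* × √(37 × 38 / 75) = *d* × 4.330. The conventional rule is positive with probability Pr(|T| > 1.993), which is the usual power. The rule as written is positive with probability 1 − power.

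| *d* (assumed) | Noncentrality | Positive under P < 0.05 | Positive under P > 0.05 |
|---|---|---|---|
| 0 | 0 | 5.0% | 95.0% |
| 0.3 | 1.299 | 24.9% | 75.1% |
| 0.5 | 2.165 | 57.0% | 43.0% |
| 0.8 | 3.464 | 92.8% | 7.2% |
| 1.0 | 4.330 | 99.0% | 1.0% |

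The simulation agrees: 57.0% at *d* = 0.5 and 92.8% at *d* = 0.8 under the conventional rule. A normal approximation with 37.5 per arm gives 58.1% and 93.4%, so the choice of method does not matter here.

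**Step 3: is there a design reason for the rule?** A large P value is not the goal of a superiority trial. Nor does a large P value from a difference test establish equivalence. No reading of the design makes the sentence correct.

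**The case against.** The strongest reply is that this is a one-character slip that no analyst would follow. The figure 0.05 is conventional, and the Introduction/Background uses the language of significance in its ordinary sense when it describes earlier studies. The intended meaning is therefore plain, and correcting it changes no sample size, procedure or patient risk. That is fair as a forecast of what would happen. The 95% error rate describes the rule as written and does not predict the analysis.

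Two further points stand. First, the reversal is a tendency and not a certainty: at *d* = 0.3 the literal rule would still be positive 75.1% of the time. Second, the split, the sidedness and the effect sizes are assumptions. The analysed number may also fall below 75, because patients converted to open surgery are excluded from the analysis. The 95% figure under the null depends on none of these for a continuous outcome.

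A misread symbol in the machine-read text cannot be ruled out entirely. However, the other symbols in the same section kept their meaning, and nothing points to a misreading. A look at the source file would settle it.

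These replies bear on the likely practical harm and not on whether the text is wrong. A prespecified rule should be usable as it stands. If this one is left, the reported analysis must depart from the protocol's only criterion, with nothing on file to show what was intended. Reversing the symbol alone would also leave one- or two-sided testing open, and that choice affects which results count as significant.

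**Conclusion.** The concern holds. The plan's sole decision threshold is wrong as written, nothing else in the document corrects it, and the superiority aim rules out any reading that would justify it. Followed literally, it raises the per-test type I error from 5% to 95% and turns power into its complement, so larger real effects become less likely to be declared. The 95% figure needs only a P value that is uniform under the null; the power figures are illustrative and rest on the stated assumptions. The practical risk is small because convention would probably prevail. The correction is still required, because the rule would give wrong conclusions if it were followed.

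**What to change.** Replace the final sentence of the Data analysis/statistics section with: *Tests are two-sided; a P value of < 0.05 will be considered statistically significant.* This corrects the direction and settles the sidedness in one step. It costs one sentence, has no operational consequence, and leaves the sample size unchanged because the document contains no calculation that depends on the threshold.
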